# 7. STATISTICAL METHODS AND DETERMINATION OF SAMPLE SIZE

# 7.1 STATISTICAL DESIGN - MODEL

This is a randomised, double blind, multi-centre, placebo-controlled, parallel group study to assess the efficacy, safety, tolerability, and PK of once daily oral doses of empagliflozin 10 mg and 25 mg compared to placebo in patients with T1DM as adjunctive to insulin therapy.

This is a 52 week trial; however the efficacy endpoints will be assessed primarily in a confirmatory manner on 26 week data, and only assessed at 52 weeks in an exploratory manner. All analyses will be done after final database lock at 52 weeks.

The superiority of 2 doses of empagliflozin will be tested against placebo. A Bonferroni adjustment will correct for the parallel testing of the 2 doses in order to maintain a type I error rate of 0.05. Each dose will therefore be tested at the level of  $\alpha$ =0.025 (two-sided). Following the efficacy analysis (on-treatment data only) of the primary endpoint, change from baseline in HbA1c after 26 weeks, an effectiveness analysis (on-and off-treatment data) will be performed in a hierarchical manner. If the null hypothesis is rejected for both the efficacy and effectiveness analysis the key secondary endpoints will be tested for superiority using a gatekeeping approach and sequential testing to maintain the type I error rate, see Section 7.2.

With regard to efficacy and safety endpoints, the term "baseline" refers to the last observed measurement prior to administration of any randomised study medication, the 4 week period prior to randomisation for the rate of hypoglycaemia and the run-in period from Visit 5 to Visit 6 for the mean daily insulin requirement, and CGM.

Patients who prematurely discontinue trial medication will continue to attend all visits and be followed up until the end of the trial when possible.

The randomisation will be stratified by the Visit 5 eGFR value ( $< 60 \text{ mL/min/1.73 m}^2$  versus  $\ge 60 \text{ mL/min/1.73 m}^2$ ), the Visit 5 HbA1c value (< 8.5% versus  $\ge 8.5\%$ ), and by the patients' pre-existing insulin therapy (MDI versus CSII). If necessary, and depending upon global distribution, entry of patients into a particular HbA1c stratum may be capped.

# 7.2 NULL AND ALTERNATIVE HYPOTHESES

The following testing procedure will be used to evaluate the superiority for the primary endpoint for both empagliflozin doses against placebo at the level of  $\alpha$ =0.025. The overall probability of type I error is therefore maintained at  $\alpha$ =0.05 (two-sided).

The superiority of treatment with empagliflozin to placebo will be tested for HbA1c change from baseline at Week 26, via the pairwise comparison of each individual empagliflozin dose against placebo, at  $\alpha$ =0.025 level. Both doses will be tested in parallel on the Full Analysis Set (FAS) for the efficacy analysis and on the modified Intention-to-Treat (mITT) for the

effectiveness analysis; see Section 7.3 for the analysis set definitions. Both analyses will test the same null hypothesis:

H0,1: Mean change from baseline in HbA1c (%) after 26 weeks in the empagliflozin XXmg group = Mean change from baseline in HbA1c (%) after 26 weeks in the placebo group

will be tested against

H1,1: Mean change from baseline in HbA1c (%) after 26 weeks in the empagliflozin XXmg  $\neq$  Mean change from baseline in HbA1c (%) after 26 weeks in the placebo group

where empagliflozin XXmg stands for empagliflozin 10 mg or 25 mg.

Following testing of the null hypothesis for both efficacy and effectiveness for HbA1c, within each dose group the alpha will be unequally split for testing the superiority of the key secondary endpoints. All tests will be two-sided. The null hypotheses for the key secondary endpoints are as follows:

 $H_{0,2}$ : Mean change from baseline in body weight (kg) after 26 weeks in the empagliflozin XXmg group = Mean change from baseline in body weight (kg) after 26 weeks in the placebo group

 $H_{0,3}$ : Mean change from baseline in % time in range as determined by CGM in Weeks 23 to 26 in the empagliflozin XXmg group = Mean change from baseline in % time in range as determined by CGM in Weeks 23 to 26 in the placebo group

 $H_{0,4}$ : Mean change from baseline in IQR as determined by CGM in Weeks 23 to 26 in the empagliflozin XXmg group = Mean change from baseline in IQR as determined by CGM in Weeks 23 to 26 in the placebo group

 $H_{0,5}$ : Mean change from baseline in TDID (U/kg) after 26 weeks in the empagliflozin XXmg group = Mean change from baseline in TDID (U/kg) after 26 weeks in the placebo group

 $H_{0,6}$ : Incidence rate of hypoglycaemia from Week 5 to Week 26 in the empagliflozin XXmg group = Incidence rate of hypoglycaemia from Week 5 to Week 26 in the placebo group

 $H_{0,7}$ : Incidence rate of hypoglycaemia from Week 1 to Week 26 in the empagliflozin XXmg group = Incidence rate of hypoglycaemia from Week 1 to Week 26 in the placebo group

 $H_{0,8}$ : Mean change from baseline in SBP after 26 weeks in the empagliflozin XXmg group = Mean change from baseline in SBP after 26 weeks in the placebo group

 $H_{0,9}$ : Mean change from baseline in DBP after 26 weeks in the empagliflozin XXmg group = Mean change from baseline in DBP after 26 weeks in the placebo group

[figure not shown]
One-tenth of the alpha ( $\alpha$ =0.0025) will be used to sequentially test H0,2, H0,3, H0,4 and H0,5. Nine-tenths of the alpha ( $\alpha$ =0.0225) will be used to sequentially test H0,6 and H0,7. Depending on the success of each sequential testing, the alpha will contribute towards the significance level for the sequential testing of H0,8 and H0,9 as follows:

- If  $H_{0,2}$ ,  $H_{0,3}$ ,  $H_{0,4}$  and  $H_{0,5}$  are all rejected, but  $H_{0,6}$  or  $H_{0,7}$  are not rejected then  $\alpha$ =0.0025 will contribute towards the testing of  $H_{0,8}$  and  $H_{0,9}$
- If  $H_{0,6}$  and  $H_{0,7}$  are both rejected, but  $H_{0,2}$ ,  $H_{0,3}$ ,  $H_{0,4}$  or  $H_{0,5}$  are not rejected then  $\alpha$ =0.0225 will contribute towards the testing of  $H_{0,8}$  and  $H_{0,9}$
- If all null hypotheses ( $H_{0,2}$  to  $H_{0,7}$ ) are rejected,  $H_{0,8}$  and  $H_{0,9}$  will be tested at the level  $\alpha = 0.0025 + 0.0225 = 0.025$

If at any stage a null hypothesis cannot be rejected, all subsequent tests in the same branch according to the diagram in Table 7.2: 1 will be performed in an exploratory manner only.

Table 7.2: 1 Summary of endpoint testing strategy

	Empagliflozin 10 mg	Empagliflozin 25 mg
Step 1: Primary endpoint (efficacy)	If $H_{0,1}$ is rejected at $\alpha$ =0.025 level using on-treatment data only then go to step 2, otherwise procedure is stopped and subsequent tests will be done only for exploratory purposes	If $H_{0,1}$ is rejected at $\alpha$ =0.025 level using on-treatment data only then go to step 2, otherwise procedure is stopped and subsequent tests will be done only for exploratory purposes
Bonferroni, two-sided (alpha=0.025)		
Step 2: Primary endpoint (effectiveness)	If $H_{0,1}$ is rejected at $\alpha$ =0.025 level using all on- and off-treatment data then go to step 3, otherwise procedure is stopped and subsequent tests will be done only for exploratory purposes	If $H_{0,1}$ is rejected at $\alpha$ =0.025 level using all on- and off-treatment data then go to step 3, otherwise procedure is stopped and subsequent tests will be done only for exploratory purposes

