### 7.3 PLANNED ANALYSES

To account for the testing of two doses of empagliflozin, a Bonferroni adjustment will be applied to the type I error rate and tests for the primary endpoint (efficacy and effectiveness sequentially) will be conducted at the level of  $\alpha$ =0.025 (two-sided). A gatekeeping and sequential testing strategy will then be employed for tests of the key secondary endpoints to maintain the type I error rate at the level of  $\alpha$ =0.025 (two-sided) within each dose (see Section 7.2 for details).

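### Within each dose, the testing scheme discards the alpha left after DBP is rejected; passing it to the branch still open would be a free improvement

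*Protocol*

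**What the plan says.** **Between doses.** Protocol 7.1: "A Bonferroni adjustment will correct for the parallel testing of the 2 doses in order to maintain a type I error rate of 0.05". That leaves 0.025 for either dose. Protocol 7.3 repeats this for the later tests: "A gatekeeping and sequential testing strategy will then be employed for tests of the key secondary endpoints to maintain the type I error rate". The level it names is 0.025 within each dose.

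**Within a dose.** Once HbA1c has passed both the efficacy and the effectiveness test, Protocol 7.2 sets out:

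- Branch A at 0.0025: weight (H0,2), time in range (H0,3), IQR (H0,4), total daily insulin dose or TDID (H0,5), in sequence.
- Branch B at 0.0225: hypoglycaemia rate Weeks 5–26 (H0,6), then Weeks 1–26 (H0,7).
- A fully rejected branch sends its alpha to SBP (H0,8), then DBP (H0,9). The sentence that sets this up begins "Depending on the success of each sequential testing, the alpha will contribute towards the significance level for the sequential testing of". SBP and DBP are tested at 0.0025, 0.0225 or 0.025, depending on which branches passed.

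**After a failure.** The rule begins "If at any stage a null hypothesis cannot be rejected, all subsequent tests in the same branch". Those later tests are exploratory only.

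**After DBP.** No rule is given. SAP section 4 leaves the scheme as it is and states only that the updated illustration in Protocol 7.2 is the valid one.

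**The concern.** DBP is an end point with nothing leading out of it. When it is rejected, the alpha used to reject it is free, but the written rules do not reuse it, even if hypotheses in the same dose remain open at a much stricter level.

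The loss falls mainly on branch A. The rationale for protocol amendment 2 was to highlight the importance of the CGM endpoints, yet they are tested at 0.0025, the strictest level in the plan. They may also rest on fewer patients: CGM may not be performed in every country (Protocol 5.2.5), data around paracetamol use are excluded (SAP 6.6.1.2), and patients without evaluable CGM data at both baseline and Week 26 are left out (SAP 7.5.1.3). TDID can be tested only after them.

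What is at stake is confirmatory power on these endpoints. The validity of the trial's claims is not in question.

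**Working it through.** **1. The plan's own figures reproduce.** Within a dose, 0.0025 + 0.0225 = 0.025. Over two doses, 2 × 0.025 = 0.05. For the sample size (Protocol 7.7: difference 0.3, SD 0.9, two-sided 0.025, power 90%), the normal formula is n = 2 × (0.9/0.3)² × (2.241 + 1.282)² ≈ 223.4, so 224 per arm. With the t distribution, 224 gives 89.9% and 225 gives 90.05%, which confirms 225. Then 225/0.94 = 239.4, so 240.

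**2. Levels reached within one dose, with HbA1c passed.**

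| Rejected so far | Still open | Level as written | Level if DBP's alpha is passed on |
|---|---|---|---|
| H0,6, H0,7, SBP, DBP (at 0.0225) | branch A | 0.0025 | 0.0025 + 0.0225 = 0.025 |
| H0,2 to H0,5, SBP, DBP (at 0.0025) | branch B | 0.0225 | 0.0225 + 0.0025 = 0.025 |
| One branch, but SBP or DBP not rejected | other branch | unchanged | unchanged |

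The second row is a trivial gain. The first is a tenfold increase in level.

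**3. Error control within the dose.** The levels in play depend only on which hypotheses have been rejected, never fall as more are rejected, and sum to at most 0.025 at every step. Before the first false rejection, only false nulls have been rejected. The levels of the true nulls at that moment are therefore no larger than if every false null had been rejected, and those sum to at most 0.025. By Bonferroni, the chance of any false rejection within the dose is at most 0.025. A simulation of the within-dose loop agreed: the largest per-dose error was 0.026, within Monte Carlo error of 0.025. Because no level falls, no current rejection can be lost, and none was lost in simulation.

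The unused allowance is visible. If only branch A is null in both doses, the written scheme can err only at 0.0025 per dose, or 2 × 0.0025 = 0.005 overall (0.004 simulated), against 0.05 permitted.

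**4. Power of one test once the alpha is released.** An endpoint with 80% power at 0.0025 has non-centrality 3.023 + 0.842 = 3.865. At 0.025 its power is Φ(3.865 − 2.241) = Φ(1.624) = 94.8%.

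The documents give no effect sizes for the key secondaries, so a range of assumed standardised effects with 225 per arm is shown:

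| Standardised effect | Power at 0.0025 | Power at 0.025 |
|---|---|---|
| 0.20 | 18% | 45% |
| 0.25 | 36% | 66% |
| 0.30 | 56% | 83% |
| 0.333 (HbA1c planning effect) | 70% | 90% |
| 0.40 | 89% | 98% |
| 0.50 | 99% | 99.9% |

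**5. Overall power per dose, allowing for the conditions.** The assumed non-centralities were HbA1c 3.5, IQR 3.5, SBP 3.3 and DBP 2.8, with larger values for weight, time in range and TDID. Power for IQR and TDID changes as follows:

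- Hypoglycaemia non-centrality 3.0: about 0.59 to 0.66. Another run, with slightly different values for the larger effects, gave 0.586 to 0.677 for TDID, a gain of 0.091.
- A weaker hypoglycaemia effect: about 0.59 to 0.61.
- No hypoglycaemia effect: no material change.

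**The case against.** **It is not an error.** Correct. The scheme is valid and internally consistent, and any sequential scheme whose last test leads nowhere could be improved in this way. A reader might infer that the type I error is wrong; the arithmetic above shows that it is not.

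**The gain is conditional and rests on chosen inputs.** This also stands. The 94.8% applies only after both hypoglycaemia tests, SBP and DBP have been rejected, and under the assumed effects DBP succeeds only about half the time. At a standardised effect of 0.50 there is almost nothing left to gain.

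**The diagram might contain a return arrow.** The figure and the key-secondary part of Table 7.2: 1 were not available in the text examined, so this cannot be excluded by sight. The written bullets and the exploratory-only sentence leave no room for one.

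**A tempting extension is to pass a dose's 0.025 to the other dose once the first has rejected everything.** A reader might infer that this too is free, since overall error would stay at 0.05. The documents do not support it. Protocol 7.3 promises 0.025 within each dose. With 10 mg effective and 25 mg wholly null, simulated error rises from 0.026 to 0.051 when the within-dose loop and this transfer are added, so the stated per-dose control is lost. It would also break the match with the two-sided 97.5% intervals in Protocol 7.3.1.1 and SAP 7.4.1: HbA1c could be declared significant at 0.05 while its 97.5% interval includes zero. That transfer is not recommended. The within-dose change raises neither problem.

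**Conclusion.** The point holds as one of efficiency within each dose: a free improvement. The useful case is branch A moving from 0.0025 to 0.025 after both hypoglycaemia tests, SBP and DBP succeed; the reverse case (0.0225 to 0.025) is trivial. The overall gain in IQR and TDID power is roughly 0.02 to 0.09 per dose if hypoglycaemia, SBP and DBP effects exist, and about zero without a hypoglycaemia effect. The levels and the error control follow from the written rules. The power figures depend on assumed effect sizes and correlations, and on the unseen diagram agreeing with the text.

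**What to change.** Before unblinding, amend Protocol 7.2 and its diagram, and mirror the change in the SAP:

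1. Add a rule: when H0,9 is rejected, its alpha passes to the first unrejected hypothesis of the branch still open in the same dose (H0,2 to H0,5, or H0,6 to H0,7). That branch is then tested sequentially from that point at 0.025 in total.
2. Amend the exploratory-only sentence so that tests after a failure are exploratory unless alpha is later passed back under rule 1.
3. Leave the Bonferroni split between doses, the primary tests and the 97.5% intervals unchanged.

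The cost is a paragraph, a redrawn diagram and a few lines of code. No data collection changes. Protocol 7.1 places all analyses after the final 52-week database lock, and the protocol keeps treatment assignment blinded until then, so the rule can be fixed in advance if it is adopted before that lock.

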### 7.3 PLANNED ANALYSES

To account for the testing of two doses of empagliflozin, a Bonferroni adjustment will be applied to the type I error rate and tests for the primary endpoint (efficacy and effectiveness sequentially) will be conducted at the level of  $\alpha$ =0.025 (two-sided). A gatekeeping and sequential testing strategy will then be employed for tests of the key secondary endpoints to maintain the type I error rate at the level of  $\alpha$ =0.025 (two-sided) within each dose (see Section 7.2 for details).

### c03024901-03 Trial Protocol Version 3.0

Page 79 of 144

Proprietary confidential information © 2017 Boehringer Ingelheim International GmbH or one or more of its affiliated companies

Safety analyses will be performed on the treated set (TS). The TS is defined as all patients treated with at least one dose of study medication.

The primary efficacy analysis will be performed on the FAS. The FAS is defined as all randomised patients who are treated with at least one dose of study medication, have a baseline  $HbA_{1c}$  and at least one on-treatment  $HbA_{1c}$  measurement. The effectiveness analysis of the primary endpoint will be performed on the mITT set. The mITT set is defined as all randomised patients who have a baseline  $HbA_{1c}$  and at least one post randomisation  $HbA_{1c}$  measurement.

A per protocol set (PPS) of patients following the trial protocol in essential criteria will be created for sensitivity analyses. Patients included in the FAS who have important protocol violations (IPVs) that can be expected to have a distorting influence on the assessment of the primary endpoint will be excluded from the PPS. Details regarding the definitions of IPVs will be provided in the TSAP.

Further sensitivity analyses will be based on the randomised set (RS). The RS includes all randomised patients regardless of treatment with study medication.

All analyses will be conducted in SAS® version 9.2 or later.

# 7.3.1 Primary endpoint analyses

# 7.3.1.1 Primary analysis of the primary endpoint

The primary endpoint in this trial is the change from baseline in HbA1c (%) after 26 weeks.

The primary efficacy analysis will be performed on the FAS; patients will be assigned to the treatment they were randomised to and analysed according to the stratum to which they belong (regardless of any mis-assignment based on identification of the wrong stratum). Only on-treatment HbA1c values will be included in the primary analysis for efficacy.

Mean changes from baseline in  $HbA_{1c}$  after 26 weeks will be analysed using a restricted maximum likelihood-based repeated measures approach (MMRM analysis). Analyses will include the fixed categorical effects of treatment, pre-existing insulin therapy, week and treatment by week interaction, as well as the continuous, fixed covariates of baseline  $HbA_{1c}$ , baseline eGFR and baseline  $HbA_{1c}$  by week interaction. An unstructured (co)variance structure will be used to model the within patient measurements.

If this analysis fails to converge, the following covariance structures will be tested: compound symmetry, variance components and Toeplitz. The (co)variance structure converging to the best fit, as determined by Akaike's information criterion, will be used as the primary analysis.

The Kenward-Roger approximation will be used to estimate denominator degrees of freedom. Significance tests will be based on least-squares means using a two-sided  $\alpha = 0.025$  (two-sided 97.5% confidence intervals). The residuals are assumed to have a multivariate normal

distribution with zero means and covariance matrix as specified above. The primary treatment comparisons will be the contrast between treatments at Week 26.

The statistical model will be:

 $HbA_{1c}$  change from baseline = overall mean + continuous baseline  $HbA_{1c}$  + pre-existing insulin therapy + continuous baseline eGFR + treatment + week + baseline  $HbA_{1c}$  by week interaction + treatment by week interaction + random error

Following the analysis of the efficacy estimand, an effectiveness analysis will be performed on the mITT set. This will use the same model as described for the efficacy analysis, but include all available on- and off- treatment values.

Boehringer Ingelheim BI Trial No.: 1245.69

c03024901-03 Trial Protocol Version 3.0

04 Jan 2017

Page 81 of 144

Page 82 of 144

# 7.3.2 Secondary endpoint analyses

## 7.3.2.1 Key secondary endpoints – confirmatory analyses

The analysis of change from baseline in body weight after 26 weeks will follow the strategy for the primary endpoint, MMRM, with the addition of terms for baseline body weight and baseline body weight by week interaction into the model. This analysis will be performed on the FAS, including all available on-treatment data.

The analysis of change from baseline in TDID after 26 weeks will follow the strategy for the primary endpoint MMRM, with the addition of terms for baseline TDID and baseline TDID by week interaction into the model. This analysis will be performed on the FAS, including all available on-treatment data. The baseline TDID will be calculated based on the mean daily insulin requirement during the 2 week run-in period. The TDID after 26 weeks will be calculated based on the mean daily insulin requirement over the previous 7 days (i.e. during Week 26).

The change from baseline in percentage time spent in target glucose range and the change from baseline in IQR in Weeks 23 to 26 weeks as determined by CGM will be analysed using an ANCOVA model. The statistical model will be:

<CGM endpoint> change from baseline = overall mean + treatment + pre-existing insulin therapy + continuous baseline HbA1c + continuous baseline eGFR + continuous baseline <respective CGM endpoint> + random error

Treatment and pre-existing insulin therapy are fixed classification effects and baseline HbA1c, baseline eGFR and baseline <CGM endpoint> are linear covariates. The random error is assumed to be normally distributed with mean 0 and unknown variance  $\sigma^2$ . The analysis will be performed on the FAS, including all available on-treatment data.

The analysis of the incidence rate of symptomatic hypoglycaemic AEs with confirmed plasma glucose < 54 mg/dL (< 3.0 mmol/L) and/or severe hypoglycaemic AEs per patient-year from Week 5 to Week 26 will utilise a negative binomial model, with terms for treatment, baseline rate, baseline HbA1c, baseline eGFR and pre-existing insulin therapy as fixed effects, and log (days of follow-up) as an offset. This analysis will include patients from the FAS, including all available on-treatment events from the start of Week 5 (Day 29) up to Week 26 cut-off date. The baseline rate of symptomatic hypoglycaemic AEs with confirmed plasma glucose < 54 mg/dL (< 3.0 mmol/L) and/or severe hypoglycaemic AEs will be calculated based on the event rate during the 4 weeks prior to randomisation.

The analysis of the incidence rate of symptomatic hypoglycaemic AEs with confirmed plasma glucose < 54 mg/dL (< 3.0 mmol/L) and/or severe hypoglycaemic AEs per patient-year from Week 1 to Week 26 will follow the same strategy as the analysis from Week 5 to

Week 26. This analysis will include all patients from the FAS, including all available ontreatment events from date of first study medication intake up to Week 26 cut-off date.

The analysis of change from baseline in SBP after 26 weeks will follow the strategy for the primary endpoint MMRM, with the addition of terms for baseline SBP and baseline SBP by week interaction into the model. This analysis will be performed on the FAS, including all available on-treatment data.

The analysis of change from baseline in DBP after 26 weeks will follow the strategy for the primary endpoint MMRM, with the addition of terms for baseline DBP and baseline DBP by week interaction into the model. This analysis will be performed on the FAS, including all available on-treatment data.

c03024901-03 Trial Protocol Version 3.0

Page 84 of 144

04 Jan 2017

Proprietary confidential information © 2017 Boehringer Ingelheim International GmbH or one or more of its affiliated companies

